2.2.2 Visit window definitions

For all the assessments, the visit recorded in web-based data capture (WBDC) will be used. Visit windows are not relevant for most of the study. There are only 3 defined visits: Visit 1 (Week -2), Visit 2 (Week 0) and Visit 3 (Week 4). Once a patient enters the dose reduction phase, the visit programme is individual to the patient, depending on their dosing and down-titration schedule; and so data are not summarised by further visit numbers. After the start of dose reduction, the important time points include: date of morning cortisol test (4 weeks after achieving an OCS dose ≤ 5 mg); date at which a patient reaches their final OCS dose in the OCS reduction phase; end of OCS reduction / start of maintenance phase; EOT; and follow-up. These will occur at different visits for different patients.

All data will be organized and analysed according to the visits specified in Table 1 of the CSP and as detailed in section 3 of this SAP.

2.2.3 Duplicate observations at the same visit

For all visits except baseline, if duplicate observations are collected at the same visit, the earliest record will be used for analysis. In case of retest in laboratory assessments, the retest record will be used for analysis. If duplicate observations are recorded on the same day and have no assessment time associated with at least one of them, or the same assessment time associated with both of them, the average of the two values will be selected for analysis at that visit. Any repeat or additional assessments performed will be included in the individual patient data listings.

2.3 Baseline and change from baseline

In general, the last non-missing observation prior to the first dose of study treatment will serve as the baseline measurement. If there is no value prior to the first dose of study treatment, then the baseline value will not be imputed and will be set to missing.

Unless indicated otherwise, Visit 2 (Week 0) is the planned baseline visit, for all assessments carried out at the centre.

The absolute change from baseline is computed as (*visit value* – *baseline value*). Percent change from baseline is computed as $((\textit{visit value} - \textit{baseline value}) / \textit{baseline value}) \times 100\%$. If either a visit value or the baseline visit value is missing, the absolute change from baseline value and the percent change from baseline will also be set to missing. If baseline value is zero, the percent change will be set to missing.

2.4 Handling of dropouts and missing data

Unless otherwise specified, missing data will not be imputed. All missing data will be reported to data management to be queried.

3. PRIMARY AND SECONDARY VARIABLES

The primary and supportive endpoints, the secondary endpoint ACQ-6, the exploratory endpoint PGIC, all safety data and blood eosinophil counts to the end of the OCS reduction phase will be analysed at the initial database lock, when the final patient has had the opportunity to complete the OCS reduction phase. All secondary efficacy, safety and exploratory endpoints not fully analysed at the initial database lock will be analysed through to end of the study at the second database lock, when the final patient has completed the follow-up visit at the end of the main study. The primary and supportive endpoints will not be analysed again at the second database lock unless necessitated by changes to the raw or reporting datasets. For the details of primary, secondary, safety and exploratory endpoints for the substudy, refer to the Addendum for the substudy.

3.1 Primary outcome variables

Two primary endpoints will be evaluated in this study.

The first is the proportion of patients who achieve 100% reduction in daily OCS dose that is sustained over at least 4 weeks without worsening of asthma. The second is the proportion of patients who achieve 100% reduction or a daily OCS dose ≤ 5 mg, if the reason for no further OCS reduction is AI, that is sustained as noted above.

The OCS dose reduction schedule during the reduction phase (Week 4 onwards) is presented in [Table 2](#).

Table 2 OCS down-titration approaches

Initial OCS dose/day	OCS down-titration to reach an OCS dose of:				
	20 mg	10 mg	7.5 mg	5 mg	0 mg
>20 mg	Reduction of 5 mg weekly until reaching dose of 20 mg/day	Reduction of 5 mg Q2W until reaching dose of 10 mg/day	2.5 mg Q2W until reaching dose of 7.5 mg/day	2.5 mg Q4W until reaching dose of 5 mg/day	No AI: reductions of 2.5 mg Q4W until reaching dose of 0 mg/day Risk AI: reductions of 1 mg Q4W and repeat test 2 months later ^a Complete AI: No OCS dose reduction and repeat test 3 months later ^b
>10 mg to ≤20 mg		Reduction of 5 mg Q2W until reaching dose of 10 mg/day	2.5 mg Q2W until reaching dose of 7.5 mg/day	2.5 mg Q4W until reaching dose of 5 mg/day	No AI: reductions of 2.5 mg Q4W until reaching dose of 0 mg/day Risk AI: reductions of 1 mg Q4W and repeat test 2 months later ^a Complete AI: No OCS dose reduction and repeat test 3 months later ^b
>7.5 mg to ≤10 mg			2.5 mg Q2W until reaching dose of 7.5 mg/day	2.5 mg Q4W until reaching dose of 5 mg/day	No AI: reductions of 2.5 mg Q4W until reaching dose of 0 mg/day Risk AI: reductions of 1 mg Q4W and repeat test 2 months later ^a Complete AI: No OCS dose reduction and repeat test 3 months later ^b
>5 mg to ≤7.5 mg				2.5 mg Q4W until reaching dose of 5 mg/day	No AI: reductions of 2.5 mg Q4W until reaching dose of 0 mg/day Risk AI: reductions of 1 mg Q4W and repeat test 2 months later ^a Complete AI: No OCS dose reduction and repeat test 3 months later ^b
5 mg					No AI: reductions of 2.5 mg Q4W until reaching dose of 0 mg/day Risk AI: reductions of 1 mg Q4W and repeat test 2 months later ^a Complete AI: No OCS dose reduction and repeat test 3 months later ^b

^a Risk AI means “partial AI” cortisol testing confirmed with ACTH stimulation testing. After repetition of the test 2 months later, the decision to further reduce OCS dose will be based on the morning cortisol test results. If test results are normal, the OCS dose may be reduced directly to 0 mg/day (if patient is receiving ≤3 mg); the patient will continue receiving 1 mg Q4W if still at risk. If complete AI is indicated, OCS dose will not be modified.

^b If morning cortisol test results again indicate complete AI at 3 months, the OCS dose will not be modified as this is the final attempt. If morning cortisol test results indicate risk AI, then reductions will be 1 mg Q4W and, if normal, then reductions will be 2.5 mg Q4W.

The **baseline OCS dose** is defined as the dose upon which the patient is stabilised prior to Visit 2 (Week 0). It is calculated as the total OCS dose taken at the first IP dose day.

The **final OCS dose of the OCS reduction phase** will be used to calculate the percentage reduction from baseline. It will be determined by the Investigator and recorded as the final OCS dose of the OCS reduction phase in RAVE (“Asthma Stable Dose”). The final OCS dose will be 0 mg/day or the lowest OCS dose possible in case no further OCS down-titration is allowed because of the presence of AI as measured by cortisol levels or in case of inadequate asthma control. The patient will maintain this dose for at least 4 weeks without worsening of asthma and will initiate the OCS maintenance phase on this OCS dose. If the OCS dose recorded as the final OCS dose in RAVE is not maintained for at least 4 weeks without worsening of asthma, the final OCS dose will be defined as the last stable dose prior. This dose may be the dose at a previous OCS reduction step (e.g. one step higher) or the dose recorded after recovery from an exacerbation, but it will not be a dose recorded during treatment of an exacerbation or AE. The time at which the final OCS dose was reached will be unchanged and time to first increase will be the time from this point until the OCS dose exceeds the defined final dose. The time recorded as the end of the OCS reduction phase will also be unchanged. Similarly, if a patient withdraws during the OCS reduction phase, the final OCS dose will be defined as the last stable dose prior to withdrawal. If no such dose exists, the final dose will be the baseline dose.

The **percentage reduction from baseline** in OCS dose is defined as:

$$\{(Baseline\ OCS\ dose - final\ OCS\ dose) / baseline\ OCS\ dose\} * 100\%$$

For an individual patient, if the final OCS dose (as defined above) results in a **percentage reduction from baseline** of 100% (i.e. the final dose is 0mg), that patient will be classified as having a 100% reduction in OCS dose. The proportion of such patients will be calculated as a primary outcome.

The second primary outcome is the proportion of patients who achieve 100% reduction or final daily OCS doses of ≤ 5 mg, if (and only if) the reason for no further OCS reduction is AI, sustained over at least 4 weeks without worsening of asthma.

In addition, the following key supportive outcomes will be calculated:

- The proportion of patients who achieve a **final OCS dose** of ≤ 5 mg, sustained over at least 4 weeks without worsening of asthma.
- The proportion of patients who achieve the following **percentage reductions from baseline** in OCS dose:
 - $\geq 90\%$ reduction
 - $\geq 75\%$ reduction
 - $\geq 50\%$ reduction

- >0% reduction

Furthermore, absolute and percentage change from baseline in daily OCS dose (mg) from the start of OCS reduction to the end of the OCS reduction phase (final OCS dose) will also be supportive variables to the primary outcome variables.

The baseline OCS dose and the final OCS dose of the reduction phase will be defined in the same way as outlined above. The absolute and percentage change will be calculated as detailed in section 2.3.

Note that for prednisone doses below 5 mg, if the exact dose strength is not available in the country, the daily dose could be achieved by dosing every other day. The daily dose will be the average of the 2 consecutive days.

3.2 Secondary outcome variables

3.2.1 Change in daily OCS dose in maintenance phase

The final OCS dose in the maintenance phase should not be associated with an asthma exacerbation or adverse event. If the OCS dose recorded at the EOT/IPD visit is to treat an asthma exacerbation or AE (therapy reasons including but not limited to “Asthma exacerbation per protocol”, “Non-asthma condition”, “Adverse Event”), the final OCS dose will be defined as the last maintenance dose prior. If a patient shows asthma worsening at the EOT/IPD visit (therapy reasons “Worsening of asthma, without exacerbation”, “ACQ-6”), the final OCS dose in the maintenance phase will be the OCS dose prescribed for the worsening. If a patient withdraws during the OCS reduction phase, the final OCS dose in maintenance phase will be missing.

In order to study whether benralizumab benefits are maintained after OCS down titration or withdrawal, the absolute change in daily OCS dose from the end of the OCS reduction phase to the end of the maintenance phase (at EOT visit or IPD visit in maintenance phase) will be a secondary outcome variable calculated as follows:

$$\text{Absolute change at EOT/IPD} = \text{final OCS dose at EOT/IPD visit in maintenance phase} - \text{final dose of the OCS reduction phase}$$

3.2.2 Time to first increase in OCS dose

There are two types of increase in OCS dose: asthma-related increase and maintenance OCS dose increase. Asthma-related OCS dose increase includes any increase associated with asthma (asthma maintenance or treatment of asthma exacerbations or asthma-related AEs or signs/symptoms of AI). An increase to treat non-asthma-related AEs will be excluded. For maintenance OCS dose increase, only those which result in an increase in maintenance dose will be counted as an event. If patients have an OCS burst to treat an exacerbation but then return to the original maintenance dose, this will not count as an event. If patients have an exacerbation resulting in an increase in maintenance dose, the time of the event is the end of the exacerbation ; otherwise the time of the event is the first day of the maintenance dose

increase. Cases where patients have an ICS burst or a systemic corticosteroid burst (via intravenous / intramuscular route) to treat an asthma exacerbation will also be counted as an event of asthma-related OCS dose increase, and the start date of the exacerbation will be the time of the event.

Time to first asthma-related increase in OCS dose and time to first maintenance OCS dose increase during the maintenance phase from achieving the final OCS dose during the reduction phase will be secondary outcome variables, and are calculated as follows:

Start date of first increase in OCS dose during the maintenance phase – Date 1st achieved the final OCS dose in the reduction phase + 1.

The date that the final OCS dose of the OCS reduction phase is 1st achieved is defined as the date of the last initiation of that dose during the OCS reduction phase. The final OCS dose of the OCS reduction phase is defined in section 3.1.

If a patient withdraws from the study before reaching the first increase in OCS dose or does not increase their OCS dose by the end of the maintenance phase, the patient will be censored at the withdrawal date or at the end date of the maintenance phase, whichever is earlier.

The proportion of patients whose OCS dose is not increased due to asthma exacerbation or worsening within 6 months will be a supportive outcome variable for this endpoint. The proportion of patients whose maintenance OCS dose is not increased within 6 months will be another supportive outcome variable.

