#### **1.4.4 Maintenance phase:**

This phase will start from the time the patient reaches a complete withdrawal of OCS (or lowest possible OCS dose) without worsening of asthma control and as determined by the Investigator (based on the cortisol/ACTH stimulation results). The maintenance phase could be initiated earlier if OCS dose reduction failed due to clinical deterioration or because the patient did not recover from AI.

The length of the maintenance phase will last approximately 24 to 32 weeks. The duration of the maintenance treatment phase will depend on when the patient enters the maintenance phase relative to the dosing cycle of benralizumab. During this phase, patients will continue benralizumab Q8W for 3 doses, and then the End of Treatment (EOT) visit will be scheduled 8 weeks ( $\pm$  7 days) after the last dose of benralizumab.

Patients who have Complete AI or Partial AI at the end of the OCS Reduction phase, will undergo a final morning cortisol test (and if required, ACTH stimulation test for indeterminate result) approximately 1- 2 weeks prior to end of the OCS Maintenance phase.

If an asthma exacerbation occurs during the maintenance phase, the length of the maintenance phase will not be extended.

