### **8.5.2 Analysis of the secondary variables**

#### **8.5.2.1 Time to 1st OCS increase**

Time to first OCS increase in the maintenance phase will be summarized using median, 25th and 75th percentiles (with 95% Cis) and Kaplan Meier plots. The start time for the analysis will be the time, in the OCS reduction phase, at which the patient first reaches the minimum stable dose that is continued into the start of the maintenance phase.

Cox-regression model analysis will also be used to summarize and analyze time to first OCS increase; covariates will include at least baseline OCS daily dose and baseline eosinophil count (categorized). If a patient withdraws from the study before reaching the defined endpoint or does not reach the endpoint by the end of the study, whichever is earlier, the patient will be censored at that time point.

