4.2.6.2 Time to first increase in OCS dose

Time from achieving the final OCS dose during the reduction phase to first asthma-related OCS increase and to first maintenance OCS dose increase during the maintenance phase will be summarised, if calculable, using median, 25th and 75th percentiles with 95% CIs calculated using complementary log-log transformation and displayed graphically using a Kaplan-Meier plot. All patients who enter the OCS reduction phase (and so have a final dose in the OCS reduction phase) will be included. Besides these cumulative statistics, the number of patients with an event and the number of patients censored will be summarised at 8 week

intervals along with the probability (and 95% CI) of no increase (Kaplan-Meier statistics) at each 8 week timepoint. This analysis will be repeated for patients who achieve 0 mg final OCS dose in reduction phase, and patients who achieve >0%, >=50%, >=75%, and >=90% OCS dose reduction in the reduction phase. For both types of time to first OCS dose increase, the number and percentage of patients with events will be summarised by the reason for the increase.

A Cox proportional hazard model will also be used to analyse time from achieving the final OCS dose during the reduction phase to the two types of first OCS increase during the maintenance phase defined in section 3.2.2; covariates will include baseline OCS daily dose and baseline categories of blood eosinophil count. If a patient withdraws from the study before increasing OCS dose or does not increase their OCS dose before the end of the maintenance phase, the time will be censored at the time of withdrawal / end of maintenance phase as applicable. The assumption of proportional hazards will be tested for covariates and appropriate action taken if the assumption is not met. The adjusted median time to the two types of 1st OCS dose increase, with 95% CI, will be reported, if calculable.

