The number of patients whose OCS dose is not increased and the number of patients whose OCS dose is increased due to asthma exacerbation or worsening within 6 months during the maintenance phase will be presented. Proportions will be reported along with their estimates, and two-sided 95% confidence interval, calculated using the Kaplan-Meier time to event analysis (with 95% CI based on Greenwood's method). The number of patients with and without maintenance OCS dose increase within 6 months will be analysed in the same way. For both summaries, patients censored at the 6 month point will be summarised as still on study / in follow-up; completed study prior to 6 months; or withdrawn from study prior to 6 months.

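### Time to first OCS increase is clocked from reaching the final dose but counts only maintenance-phase increases, so the interval between the two is event-free by construction

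*SAP*

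**What the plan says.** **Clock and event.** SAP 3.2.2 sets the time as "Start date of first increase in OCS dose during the maintenance phase – Date 1st achieved the final OCS dose in the reduction phase", plus one day. It dates the final dose at its last initiation in the reduction phase. Protocol 8.5.2.1 uses the same origin: the time in reduction "at which the patient first reaches the minimum stable dose that is continued into the start of the maintenance phase".

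**Who is analysed.** SAP 4.2.6.2 states: "All patients who enter the OCS reduction phase (and so have a final dose in the OCS reduction phase) will be included". It plans Kaplan-Meier probabilities every 8 weeks and a Cox model, and mentions no delayed entry. It also plans a supportive count of patients with and without an increase due to "asthma exacerbation or worsening within 6 months during the maintenance phase will be presented", estimated by Kaplan-Meier.

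**When maintenance starts.** Protocol 1.4.4 says "This phase will start from the time the patient reaches a complete withdrawal of OCS (or lowest possible OCS dose") and 4.2.3 agrees. Protocol 5.1.2.1 instead makes the final dose one that has stayed unchanged for 4 weeks, with maintenance following.

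**Complete AI.** Under Protocol 1.4.3 and 5.2.1.1, patients are tested after 4 weeks on 5 mg. With complete AI the dose is held and the test repeated 3 months later. If AI is still complete, the patient then moves to maintenance.

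**Redefined final doses.** If the recorded final dose does not hold for 4 weeks, SAP 3.1 substitutes the last stable dose, keeps the date, and says "time to first increase will be the time from this point until the OCS dose exceeds the defined final dose". For patients who withdraw during reduction it uses the last stable dose; "If no such dose exists, the final dose will be the baseline dose".

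**The concern.** The risk set opens before the event can occur. A lasting increase before maintenance either changes the final dose or resets the start date through the last-initiation rule. A burst before maintenance falls outside the event window. Neither can be an event, yet the time counts as time at risk. Patients who leave during reduction are included too, and are censored although they could never have had a countable event.

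This is a key outcome measure for the secondary objective of sustained reduction over about 6 months after down-titration (SAP 1.1.2). The 6-month proportion is described as a maintenance-phase quantity but is given no clock of its own.

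Two gaps in the definitions add to this. SAP 3.1 sets no maintenance-phase limit, while SAP 3.2.2 does. And a patient who never leaves the baseline dose does not initiate it in the reduction phase, so has no defined start date.

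**Working it through.** **1. Maintenance length, as stated.** The first maintenance dose falls 0 to 8 weeks after entry, then come two 8-week intervals, then EOT 8 weeks later: 0+8+8+8 = 24 to 8+8+8+8 = 32 weeks. This matches the protocol's 24 to 32.

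**2. Gap with complete AI at both tests.** Three months is 3 × (365.25/12)/7 = 13.0 weeks.
- Tapered to 5 mg: 4 + 13.0 = 17.0 weeks.
- If one or two ACTH tests are needed, at about 1 week each: 18 to 19 weeks.
- Baseline 5 mg, never reduced: 13.0 weeks if dated from Visit 3, 17.0 if from Week 0; the plan defines neither.

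Six months is 26.1 weeks, so a 17-week gap takes up 17.0/26.1 = 65% of the 6-month window.

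**3. Gap for most others.** It is 0 weeks under Protocol 1.4.4 and 4.2.3, and about 4 weeks under 5.1.2.1. The stated total durations (about 32 weeks for a 5 mg baseline, about 48 for 40 mg) do not settle which. Benralizumab falls at weeks 0, 4, 8, 16, 24, 32, 40 and 48. On the fastest taper, 0 mg is reached at week 8 (5 mg baseline) or week 25 (40 mg baseline).
- No gap, adding the minimum 24 weeks: 8+24 = 32 and 25+24 = 49.
- 4-week gap, 5 mg baseline: entry at week 12, doses at 16, 24 and 32, so the last dose is at week 32 and EOT at week 40.
- 4-week gap, 40 mg baseline: entry at week 29, doses at 32, 40 and 48, so the last dose is at week 48.

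The stated figures fit the first reading as time to EOT and the second as time to last dose.

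**4. Effect on Kaplan-Meier.** The documents give no event rate or AI share, so these inputs are assumed: a constant hazard, equal in all patients, and S0 = 0.75 as the true 26-week increase-free proportion from maintenance start. With a gap of w weeks, the reported value at week t is S0^(max(t−w, 0)/26).

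| Week t | w = 0 | w = 4 | w = 17 |
|---|---|---|---|
| 8 | 91.5% | 95.7% | 100% |
| 16 | 83.8% | 87.6% | 100% |
| 26 | 75.0% | 78.4% | 90.5% |

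With 15% of patients at 17 weeks:
- others at 0: 0.85 × 0.750 + 0.15 × 0.905 = 77.3%
- others at 4: 0.85 × 0.784 + 0.15 × 0.905 = 80.2%

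With 5% the range is 75.8% to 79.0%; with 25%, 78.9% to 81.4%. At a 15% share, a true 60% reads 63.6% to 67.7%, and a true 90% reads 91.0% to 92.2%.

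**5. Effect on Cox.** In simulation (400,000 patients, maintenance length uniform on 24 to 32 weeks), a true hazard ratio of 1.0 reads roughly 0.86 to 0.90 if 25% of one covariate group and 5% of its reference have the 17-week gap. With the shares reversed it reads 1.12 to 1.15. A 4-week gap common to all leaves the hazard ratio unchanged.

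**6. Remedies, same simulation, 26-week Kaplan-Meier.**

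| Gaps | Planned | Delayed entry, planned origin | Clock from maintenance start |
|---|---|---|---|
| 15% at 17, others 0 | 77.3% | 75.0% | 75.0% |
| 15% at 17, others 4 | 80.2% | 78.4% | 75.0% |
| All at 4 | 78.4% | 78.4% | 75.0% |

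Delayed entry removes the distortion from unequal gaps. It does not remove a gap shared by everyone.

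**The case against.** The origin is deliberate. The listed outcome measure is time to an increase after the minimum dose is achieved, Protocol 8.5.2.1 says the same, and the SAP amendment history (24 May 2019, item 11) records the move away from maintenance start. For a quantity measured from the final-dose date, 78.4% at 26 weeks with a common 4-week gap is not in itself an error. This stands: the origin may be kept. What it does not justify is counting patients as at risk while no event can be recorded, or describing the result as maintenance-phase durability.

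Several passages start maintenance on reaching the dose. If that governs, most patients have no gap and the lower figures apply. This also stands, which is why the size is given as a range.

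A reader might infer that every patient with complete AI has a 17-week gap. The documents do not support that: those who recover at the repeat test resume tapering and reach their final dose later. A burst followed by a return to 5 mg may also restart the clock and shorten the gap, although the burst is still not counted.

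The planned repeat in patients reaching 0 mg excludes the 17-week group, leaving only the 0-or-4-week question there. The effect on medians may be moot: with S0 = 0.75, survival at 32 weeks is 0.75^(32/26) = 70%, so no median is reached, and the SAP reports it only if calculable.

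**Conclusion.** The mechanism follows directly from the plan's text: following it as written biases the increase-free proportions towards durability wherever a gap exists. The gap of about 17 weeks applies to patients tapered to 5 mg with complete AI at both tests. In that group the 8- and 16-week estimates are 100% by definition.

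On the illustrative inputs the overall 26-week figure rises by 2.3 to 5.2 points. The upper end needs both the 15% share and the 4-week reading. All rates and shares are assumptions, so these are not estimates for this trial. The Cox figures likewise show only that distortion can go either way.

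It would be too much to infer that the trial's main conclusions are at risk. No hypothesis test or sample size rests on this endpoint. The primary endpoints, the dose change across maintenance and the maintenance-phase exacerbation rates do not use this clock. It should be corrected because it is a key secondary measure and the correction is cheap.

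**What to change.** 1. Reconcile Protocol 1.4.4 and 4.2.3 with 5.1.2.1 on when maintenance starts. Reconcile SAP 3.1 with 3.2.2 on whether increases outside maintenance count, and define a start date for patients who never leave the baseline dose.
2. In the Kaplan-Meier and Cox analyses, count patients as at risk only from maintenance start. Either use delayed entry at that date, which keeps the protocol origin, or start the clock there and list the departure from Protocol 8.5.2.1 in SAP section 6. Show the number who leave during reduction alongside.
3. Measure the 6-month proportion described as a maintenance-phase result from maintenance start. Delayed entry alone would not correct it if a gap is common to all.

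**Cost.** SAP wording and, for the second option, a section 6 entry. No new data are needed: the maintenance start date is already used in SAP 3.3.2 and 4.2.4. Results become conditional on entering maintenance, and the durability figure becomes slightly less favourable. Precision at 6 months falls somewhat: if maintenance lengths are uniform on 24 to 32 weeks, (26 − 24)/8 = 25% of event-free patients are censored before 26 weeks from maintenance start.
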